### A. Introduction:

This is a pilot study to determine whether prolonged continuous peripheral nerve blockade, given for a duration longer than is customary in clinical practice, can reduce the incidence of chronic pain after ankle fracture. Patients undergoing surgery for open reduction and internal fixation of ankle fractures will be randomized to standard care (single shot peripheral nerve block prior to surgery) or experimental (the same single shot nerve block, followed by continuous popliteal nerve block with ropivacaine starting just after surgery). The primary outcome will be scores on a

validated ankle/foot pain questionnaire that includes questions on function (Self-Administered Foot and Ankle Questionnaire, SEFAS). Subjects will be followed for one year, with SEFAS scores administered at 14 days, and 3, 6, and 12 months following the ankle surgery. Secondary outcomes are postoperative opioid use in the Post-Anesthesia Care Unit (PACU), and pain ratings in the PACU. Data will also be obtained regarding the feasibility of doing a larger study. Preliminary analysis of possible confounding variables will be conducted, but as this is a pilot study it is anticipated that there may not be enough subjects to yield significant findings about patient subgroups.

## **B. Specific Aims and Hypotheses**

Aim 1: Test the hypothesis that SEFAS scores at the one year time point are higher (better outcome) in subjects who received a ropivacaine pump compared to patients who received standard care. This is the primary outcome measure).

Aim 2: Test the hypothesis that SEFAS scores at earlier time points (14 day, 3 month, 6 month) are higher in subjects who received a ropivacaine pump compared to patients who received standard care.

Aim 3: Test the hypothesis that pain scores and total opioid use in the PACU are lower in subjects receiving the ropivacaine pump.

Aim 4: Conduct a preliminary examination of possible roles of confounding clinical and demographic variables, focusing on: severity of ankle fracture; sex; and body mass index (BMI).

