In the experimental group, in addition to the standard single shot nerve block, subjects will receive a catheter to deliver continuous 5 day popliteal sciatic nerve block using a disposable ambulatory pain pump. The catheter will be inserted starting just prior to surgery. This procedure is readily added on to the procedure for single injection, which involves ultrasound (and in some cases nerve stimulation) guidance for insertion of a needle near the sciatic nerve at the popliteal fossa. As part of standard care for administering a peripheral nerve block, sedatives are administered on as needed basis. Typically the patient will receive midazolam 1 mg every 5 minutes as needed. The catheter is inserted

just after the nerve block injection, during the same procedure and using the same needle placement. If there is a major vascular injury during the catheter placement (placement of the peripheral nerve catheter into the artery as confirmed by withdrawal of blood from the catheter itself), the catheter will be withdrawn and the subject will not receive a pump. An ambIT portable pump (as currently used in the participating hospitals after some other types of surgeries) will be attached to the catheter at the time the block is placed, and continuous block with 0.2% ropivacaine will begin immediately after surgery. The drug delivery rate will be 6 mL/hour. An 800 mL bag of medication will be provided to the subjects to allow medication for a 5 day period without requiring the subject to return to the clinic for refill. This drug delivery rate is on the lower end of the range commonly used in our hospitals for patients taking home pumps after other types of surgeries, which are usually started at 8 mL/hour with the option of patient controlled boluses. Previous clinical studies examined infusion rates of 6 to 14 mL/hour. The lower, fixed rate was chosen for this study to help avoid toxicity, since the duration of the pump is longer than commonly used at our hospitals. The goal based on preclinical studies is to block abnormal spontaneous activity from the sensory nerves, which requires a lower dose than complete sensory block. The selected infusion rate should also avoid motor block. The daily dose will be 384 mg; the FDA data sheet [19] indicates that a cumulative dose of up to 770 mg over 24 hours is well tolerated and studies indicate that the peak systemic levels during prolonged infusion occur after approximately 3 days[12].

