Randomization: We will use a block-stratified randomization schedule with blocks of sizes 2 and 4. The West Chester and Uptown locations will have separate randomization schedules as it is thought the two locations provide somewhat different populations, making it desirable to have approximately equal numbers in the control and experimental groups at each site. Due to the requirement for quarantine of the ropivacaine prepared by IDS, subject randomization may sometimes deviate from the schedule: a subject scheduled to receive a pump may be placed in the control group if no ropivacaine is available at the time of their surgery, which will be compensated by placing a subsequent subject scheduled to be in the control group into the experimental group when drug is available. These deviations will not be based on subject characteristics, so that assignments remain random, and the total number of control and experimental subjects at each site will remain the same.

Data collection: We will establish an online copy of the SEFAS which subjects can use to enter their responses. This will be done using the REDCap (Research Electronic Data Capture) system for secure web based capture of questionnaire data. For patients opting to have a link to the SEFAS sent to their cell phones, the REDCap-Twillio integration platform will be used. Patients electing not to use the online entry format will be contacted by the research nurse via the preferred route indicated on the consent form, and the research nurse will then enter the data into the Redcap project database. Data from the questionnaires will be exported out of REDCap to be merged with the data from the Medidata Rave® database for analysis. All other data will be entered directly into the Medidata Rave® clinical database. Clinical demographic data will be obtained from the patient at the beginning of the study and verified with the electronic medical record. Analgesic use in the perioperative period will be obtained from the electronic medical chart. Patients typically receive acetaminophen and celecoxib preoperatively, then opioids postoperatively as needed. However, participating in the study will not affect the subjects' options for treatment for pain. Numerical pain ratings recorded in the PACU will be obtained from the electronic medical chart. The Verbal Numerical Scale (VNRS, 0 = no pain, 5 = moderate pain, 10 = worst possible pain) is used for patients in the

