Fatigue	No interference with activity	Some interference with activity	Significant; prevents daily activity	ER visit or hospitalization
Myalgia	No interference with activity	Some interference with activity	Significant; prevents daily activity	ER visit or hospitalization

Table 9.4 extracted from: Guidance for Industry, Toxicity Grading Scale for Healthy Adult and Adolescent Volunteers Enrolled in Preventive Vaccine Trials, U.S. Department of Health and Human Services, Food and Drug Administration, Center for Biologics Evaluation and Research, August 2016

Treatment of cardiovascular and neurologic adverse events

- Local anesthetic systemic toxicity
 - Treatment will be initiated as recommended as the American Society of Regional Anesthesia and Pain Medicine, according to the society's checklist

Treatment will include: transfer to intensive care unit setting if not already in intensive care unit, continuous hemodynamic monitoring for at least 24 hours, appropriate airway management with assistance from respiratory therapy and a critical care consultant as needed, cardiovascular stabilization and assistance from a critical care consultant as needed, administration of Lipid Emulsion therapy, as per ASRA checklist in Appendix, Neurology consult for any observed systemic

neurologic toxicity (including change in vision, mental status change, persistent headache, seizure), Cardiology consult for any arrhythmias that persist greater than 30 minutes, beyond initial appropriate medical treatment, or result in hypotension with systolic blood pressure < 80mmHg.

Every adverse event, whether or not thought to be related to study drug, will be recorded and entered into the Medidata Rave® Case Report Form database.

Any medical condition present prior to study enrollment should not be reported as an adverse event, unless the medical condition worsens in severity or seriousness during the study. In this case it may be reported as an adverse event at the discretion of the Investigator.

The Investigator will review each event and assess its severity and relationship to the study treatment.

Criteria for stopping the study early:

Because this is a small study, criteria for stopping the study will not be based on statistical analysis but rather on the occurrence of any of the following serious adverse events in any of the subjects randomized to receive the ropivacaine pumps:

During immediate peri-operative period after pump has been connected:

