##### **D1. Aim 1:**

Each SEFAS response has 5 ordinal response choices scored 0 through 4. With 12 items and with the lowest score (0) representing the most severe disability, the total score ranges from 0 to 48. If a subject omits one or more questions, the total score will be re-normalized to 48. Group differences in the SEFAS scores at the 12 month time point will be analyzed using the t-test or Mann-Whitney test, as appropriate.

Patients who are withdrawn from the study due to failure of the initial nerve block will be considered as screening failures; no follow-up data or questionnaire scores will be obtained. The same approach will be taken for patients who decide to withdraw from the study, or are withdrawn by the attending surgeon or anesthesiologist, after randomization but before the single shot nerve block procedure.

Patients lost to follow-up after the end of the 5 day nerve block will be analyzed with a per-protocol analysis. We consider that, since the follow-up begins after the end of the treatment and consists only of completing questionnaires, there is unlikely to be a bias towards the experimental or control group having drop-outs.

Patients who have to (or choose to) remove the pump before the entire 5 day treatment period will be analyzed both an intent-to-treat analysis and a per-protocol analysis. The duration of pump use will be noted.

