**E. Variables in the analysis data set with Definitions**

Description
Patient unique ID
Age at ankle surgery
Date of ankle surgery
Weight and height at time of surgery
Date of enrollment
Gender
Race
Ethnicity
Randomized to control or experimental group?
Ankle fracture: number of malleoli affected
Grade of injury (defined as :closed injury, or open injury with Gustilo Anderson classification grade 1, grade 2, grade 3a, grade 3b, grade 3cr)
Opioid medication use in PACU: time, agent, dose, and route for each administration
Times entered and discharged from PACU
PACU discharge status (home, rehab facility, hospital, AMA)
Verbal pain scores in PACU (0 – 10 scale) and times at which recorded
Surgical Hardware: number of plates implanted, length and number of screw holes of each.
Estimated blood loss during surgery
Pain medication prescription at discharge (drug, dose)
Start time of surgery
End time of surgery
SEFAS score (2 week, 3, 6, 12 month post surgery)
Subject-reported analgesic use (2 week, 3, 6, 12 month post surgery)
Dates of post-surgical follow-ups (FU)
Weight bearing recommendation at each FU (non, partial, full, other)
Weight bearing current status at each FU [full, assisted (cane, walker, boot), non (crutch)]
Pain status at each FU (none, mild, severe)
Pain medication prescriptions at each FU (drug, dose)
Wound healing status at each FU (dehiscence, cellulitis , deep infection, healing well, other)
Range of motion at each FU
Re-operation required?
Date of re-operation

Indication for re-operation (infection, non-union, hardware failure, hardware removal, other)
Chronic pain conditions diagnosed at one year FU.

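### The SAP aims group subjects by pump received while its data set holds only the randomised arm, and subjects assigned a pump who never start it have no analysis rule; this can bias the SEFAS comparison

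*SAP*

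**What the plan says.** **Grouping in the aims.** SAP section B, Aim 1, which it names as the primary outcome measure, says one-year SEFAS scores are "higher (better outcome) in subjects who received a ropivacaine pump compared to patients who received standard care". Aim 2 uses the same comparison at the earlier time points. Aim 3 says PACU pain scores and opioid use are "lower in subjects receiving the ropivacaine pump".

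**Grouping in the data set.** SAP section E lists one arm variable, "Randomized to control or experimental group". Neither section E nor section F has a field for whether a pump was started or for how long it ran, although D1 says the duration of pump use will be noted.

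**Analysis text.** SAP D1 says: "Group differences in the SEFAS scores at the 12 month time point will be analyzed using the t-test or Mann-Whitney test, as appropriate". It names no analysis set for that comparison. It has rules for a failed initial block, withdrawal between randomisation and the block, loss to follow-up after the 5 days, and early pump removal. Only the last group "will be analyzed both an intent-to-treat analysis and a per-protocol analysis".

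**Assigned a pump, never started.** Protocol section 6 says that if the catheter enters the artery, "the catheter will be withdrawn and the subject will not receive a pump"; it does not say whether the subject is then followed. The safety criteria in protocol section 10 say subjects are discontinued or removed for blood in the catheter, for an inadequate ultrasound view, unresolved paresthesia or signs of systemic toxicity, or if the catheter comes out during surgery or in the PACU. The same section keeps subjects who remove a pump early in the study for the surveys.

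**Stock swaps.** Protocol section 7, Randomization, says "a subject scheduled to receive a pump may be placed in the control group if no ropivacaine is available at the time of their surgery", with a compensating placement in the other direction later.

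**The concern.** The aims, the data set and the analysis text do not settle who belongs to the pump group. For most subjects this makes no difference. It matters for a subject assigned to the pump, with a working block, who never starts the infusion. The experimental arm is the standard block plus a pump, so this subject has in fact received standard care. Aim 1 read literally counts the subject as a comparator, the data set says experimental, and protocol section 10 suggests the subject leaves the study.

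The catheter events cannot happen to a control. If the subjects affected differ in prognosis, for example because of difficult anatomy or a complicated procedure, grouping by receipt or dropping them removes them from the pump arm while their counterparts stay in control. The trial is open label, and without a rule the grouping could be chosen after results are known. The pilot also aims to estimate incomplete treatment for a full-sized study (protocol section 12), which needs a record of who started the pump.

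**Working it through.** **The plan's own figure.** Protocol section 12 says 20 per group detects 9 SEFAS points with power 0.8 at alpha 0.05. The SD is cited but not given, so the figure cannot be reproduced independently. Solving backwards (two-sided, 20 per group, 9 points, power 0.80) gives an SD of 9.90 with the t-test and 10.16 with the normal approximation. I use 9.90 as an assumption. The standard error of the difference is then 9.90 × √(2/20) = 3.13 points.

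**Bias under no true effect.** Assume each arm of 20 holds k subjects of the kind who would not get a pump if assigned one, and that they score g points below the rest in either arm. Set the mean of the rest to 0.

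- *Analysed as assigned:* both arms average −kg/20, so the expected difference is 0.
- *Dropped from the pump arm:* pump mean 0, control mean −kg/20. Spurious gain = kg/20.
- *Counted as controls:* pump mean 0; the comparator has 20 + k subjects, of whom 2k carry the deficit. Spurious gain = 2kg/(20 + k).

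| k | g | Dropped | Counted as controls |
|---|---|---|---|
| 1 | 5 | 1×5/20 = 0.25 | 10/21 = 0.48 |
| 1 | 10 | 1×10/20 = 0.50 | 20/21 = 0.95 |
| 2 | 5 | 2×5/20 = 0.50 | 20/22 = 0.91 |
| 2 | 10 | 2×10/20 = 1.00 | 40/22 = 1.82 |

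The largest entry is 1.82/3.13 = 0.58 of a standard error, or 1.82/9 = 20% of the design effect. The smallest is 0.25/3.13 = 0.08 of a standard error. Enrolling replacements, which the ceiling of 60 allows, restores the numbers but leaves the dropped-subject bias at kg/20.

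**Cost of analysing as assigned.** If the pump truly adds 9 points and m of 20 assigned subjects never start it, the expected difference is 9 × (1 − m/20): 8.55 for m = 1 and 8.10 for m = 2, or 0.45 points per subject. Power by the t-test at SD 9.90 goes from 0.80 to 0.76 and 0.71.

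**How likely k is.** Protocol section 10 lists bleeding or blood aspiration at 0.4%. For 20 pump subjects that is 20 × 0.004 = 0.08 expected, and 1 − 0.996^20 = 7.7% for at least one. The documents give no rate for the other routes to not starting the pump, such as an inadequate view or catheter loss, so the total is unknown.

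**The case against.** The strongest reply is that the wording of the aims is shorthand. SAP sections A and C describe randomised groups, the Aim 3 and Aim 4 methods speak of experimental and control, the mock tables are headed Control and Experimental, and no as-received analysis is listed. That is a fair reading and probably the intended one. It does not supply the missing rule, because D1 still names no analysis set and says nothing about a subject who never starts the pump.

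Three stronger inferences are tempting and are not supported.

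- *That the intent-to-treat sentence contradicts Aim 1.* It covers only early pump removers, who were both assigned and given a pump and are in the pump group either way.
- *That stock swaps dilute the effect.* If swapped subjects were analysed by their original list slot, one, two or three swapped pairs would cut the expected difference to 8.1, 7.2 or 6.3 points, and power to 0.70, 0.58 or 0.46 (t-test, SD 9.90, allowing for the mixed arms). No passage plans that analysis. The protocol says randomisation may deviate from the schedule, so the randomised group is most naturally the one the subject was placed in. For a swap, placement and receipt agree. What remains is that the recorded arm is not stated explicitly.
- *That the grouping is shown to change the SEFAS result.* It can do so. With no swaps and no subjects who fail to start the pump, all groupings are identical.

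It is also fair to object that the quoted route, arterial placement, is rare on the protocol's own figure, and that a 10-point deficit has no source and exceeds the 9-point design effect. Both points limit the likely size and are why a range is given.

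**Conclusion.** The point holds as a gap in definition with a potential for bias. The aims are worded by receipt, the data set records only randomisation, and subjects assigned a pump who never start it are not covered by the analysis text. With one or two such subjects among 20, a deficit of 5 to 10 points and no true effect, the spurious gain for the pump is about 0.25 to 1.0 points if they are dropped and about 0.5 to 1.8 if they are counted as controls. Neither the number nor the deficit is in the documents. This is modest beside a standard error of about 3.1 points (itself resting on an assumed SD), but it favours the pump whenever these subjects have the worse prognosis, and it is avoidable. It should be corrected before analysis; it does not undermine the design.

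A separate inconsistency concerns the stopping criteria in protocol section 10. They are introduced as applying to "serious adverse events in any of the subjects randomized to receive the ropivacaine pumps", while a later item refers to subjects who are receiving pumps. A reader might infer that a control moved to the pump by a stock swap escapes the criteria. On the natural reading of the randomisation text, that subject counts as randomised to the pump, so the inference does not follow. The passages should still be reconciled; no wording is proposed here.

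**What to change.** 1. Reword SAP Aims 1 to 3 to compare subjects assigned to the pump arm with subjects assigned to standard care.
2. In SAP D1, define the primary analysis arm as the assignment issued before the block procedure, after any stock swap, and kept whether or not the pump is started.
3. State that subjects with a working block who never start the pump are followed for SEFAS and analysed in their assigned arm. Reconcile protocol sections 6 and 10 on whether these subjects are followed.
4. In SAP section E, replace the single arm field with list assignment, issued assignment, and pump started (yes/no, with duration). Report an analysis by pump started as a sensitivity analysis only.

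The cost is wording, a few extra data fields, and questionnaires for a small number of subjects who might otherwise have left the study. No extra patients or procedures are needed. The drawback is some dilution of the primary estimate, about 0.45 points per subject who never starts the pump if the true effect is 9.

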## **C. Study Design**

This is an investigator-initiated, single-center, prospective, non-blinded, randomized pilot study. We are authorized to enroll up to 60 patients to allow for 40 evaluable subjects.

Adults undergoing surgery for open reduction and internal fixation for traumatic ankle fracture will be invited to participate in the study comparing the 2 forms of nerve block. All patients are currently given the option of popliteal nerve block (single injection of ropivacaine given just prior to surgery), which helps provide pain relief in the immediate postoperative period; the surgery itself is done under general anesthesia. Participants who have agreed to have the single shot procedure will be randomized into the control group (standard-of-care single popliteal injection of local anesthetic just prior to surgery) or experimental group (standard-of-care single injection plus 5 day ambulatory popliteal nerve block).

The treatment will be open label due to the impracticality of blinding the physician or patient to the presence of local anesthetic in the 5 – day pump and the ethical barriers to subjecting patients to implantation of a catheter and empty or saline pump with no benefit to them. Per standard of

care, patients in both the experimental and control groups will also have other oral pain medications prescribed for use as needed.

Standard-of care procedures will be used for placement of the single shot popliteal nerve block. In the experimental group, in addition to the standard single shot nerve block, subjects will receive a catheter to deliver continuous 5 day popliteal sciatic nerve block using a disposable ambulatory pain pump. The catheter will be inserted just prior to surgery. A portable pump will be attached to the catheter at the time the block is placed, and continuous block with 0.2% ropivacaine will begin immediately after surgery when the patient arrives in the PACU.

Additional data routinely obtained for clinical purposes will also be collected including demographic variables, analgesic use in the PACU, and details of the ankle fracture and surgery.

The standard follow-up appointments with the orthopedic surgeons following ankle surgeries are at 10 - 14 days, 5 – 6 weeks, and 3 – 4 months. Chart review of these follow-up appointments will be used to extract additional clinical variables.

Subjects will be contacted at approximately 14 days and 3, and 6, and 12 months following the surgery to complete a pain questionnaire, the SEFAS. The SEFAS is designed to evaluate disorders of the foot and ankle. It does not require physician input, and a study of its use after surgery found it to be a valid, reliable, and responsive patient-oriented outcome measure. It consists of 12 questions focusing primarily on pain and its functional impact on daily life activities. Subjects will also be asked to provide information about their medication use including pain medications, at each of these time points.

Inclusion criteria –

- Adult patients of either sex, age 18 to 65
- Referred for surgery for open reduction and internal fixation for ankle fracture
- Agreed to have a single shot local nerve blockade (routinely offered as part of the standard-of-care but declined by some patients)

Exclusion criteria:

- patients unable to give informed consent in English
- unable to complete surveys in English
- unable to understand instructions for using the pump in English
- likely to be unavailable for follow-up
- polytrauma; undergoing other surgeries or having other orthopedic injuries related to the precipitating cause of the ankle fracture
  - infection
  - peripheral vascular disease
  - diabetes
  - undergoing chemotherapy
  - pregnancy or refusal to take pregnancy test, if of childbearing potential
  - lactating
  - have heart disease or heart rhythm disorder or taking anti- antiarrhythmic drugs

- severe renal impairment (Class 3 or worse kidney disease)
- liver disease (cirrhosis or liver failure)
- ever had an allergic reaction to any type of local anesthetic
- taking therapeutic doses of anti-coagulants or anti-platelet therapy (prophylactic doses started because of the hospital admission are not an exclusion)
- taking antidepressants or other psychiatric medications (due to drug interaction risk per the ropivacaine data sheet)
- single shot local nerve block prior to surgery was ineffective (rare)
- selected for neuraxial anesthesia rather than general anesthesia for the open reduction surgery (rare)
- already receiving chronic analgesic therapy for a separate chronic pain condition

